### 4.2.2 Spatiotemporal Measures

Variables = **STANCE**  
**SWING**  
**DS**  
**StrLENSYM**

**StrLENGTH**  
**StrVEL**  
**10MWTIME**

**Assessed at time points 1,2,6,7, and 8 during a series of 3 instrumented 10-meter walk tests.**

Participants will be instrumented with APDM® inertial sensors and perform a series of three, 10-meter walk tests (10MWT). Once sensors are placed, individuals will begin the test in a standing position at one end of a marked 14-meter path. They will be asked to walk to a line at the end of the marked path using the instructions, “*Please walk at a comfortable pace to the line at the other end of the hallway. Do you see the line?*”. A member of the research team will tell the participant when to begin. A 10-meter section at the middle of the path will be labeled. A stopwatch will be used to time the participant during ambulation of the middle 10-meters. Time of ambulation for 10MWT (10MWTIME) will be recorded on paper forms. Other variable data (STANCE, SWING, DS, StrLENSYM, StrLENGTH, StrVEL) will be downloaded in .csv file format from APDM® Mobility Lab software.

Mean values of the three trials will be calculated:

$$\text{Mean} = (10\text{MWT}_{\text{Trial1}} + 10\text{MWT}_{\text{Trial2}} + 10\text{MWT}_{\text{Trial3}})/3$$

Mean values will be reported directly (10MWTIME, DS, StrLENGTH, StrVEL), or used to calculate symmetry ratios.

Symmetry ratios will be calculated from the mean values as follows:

$$\text{STANCE Symmetry Ratio} = (\% \text{ of time in Stance Paretic/Non-Paretic Limb})$$

SWING Symmetry Ratio = (% of time in Swing Paretic/Non-Paretic Limb)  
StrLENSYM Symmetry Ratio = (Stride Length Paretic/Non-Paretic Limb)

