METHODS: Participants will undergo a series of three assessments within a one week time frame prior to initiating intervention. Intervention using the TPAD and overground training will occur the following week for five consecutive visits. On completion of the final training visit, participants will be re-assessed, and return for a single follow up visit the next week for the final assessment. Each study visit will be approximately 1-1.5 hours in duration, and total participation should be completed within three weeks.

EXPECTED OUTCOMES: We anticipate this training paradigm will prove feasible in reducing both load and stance asymmetry in a population of individuals with chronic stroke.

II. Research Questions:

- 1) Is a five day gait training program using the TPAD and incorporating augmented visual feedback and an overground walking component feasible in terms of safety, treatment tolerance, and adherence in individuals with chronic stroke who present with gait asymmetry?
- 2) Is this training program effective at improving load force symmetry after five sessions?
- 3) Is this training program effective at improving stance time symmetry in overground gait?

III. Study Design/Methodology

This is a single arm, non-randomized pilot study of feasibility. The study population and details of study procedures are specified below.

IV. Outcome Measures

A. Primary Outcomes

- Measures of Feasibility
 - Safety
 - Adverse Events / Serious Adverse Events
 - Adherence
 - Attendance Rates of Study Visits
 - Tolerance
 - Ratings of Perceived Exertion (RPE)
 - Heart Rate (HR)
- Efficacy
 - Overall Load Force Symmetry (over the course of training)
 - Stance Time Symmetry

B. Secondary Outcomes

- Daily Load Force Symmetry (intraday changes in load force)
- Time in Double Support
- Swing Time Symmetry
- Stride Length Symmetry
- Stride Velocity Symmetry
- Gait Velocity
- Balance (as per the Berg Balance Scale)

V. Study Population

A total of 12 adults (ages 18-75) will be recruited for participation from a voluntary stroke registry, anticipating 20% attrition, or that at least 10 participants will meet criteria and complete study participation.

Inclusion Criteria:

- Chronic (>6 months) stages post stroke
- History of a single stroke event (either ischemic or hemorrhagic by origin)
- Minimal score of 22 or higher on the MoCA
- Must be independent community ambulator (with/without AFO)
- May use a unilateral assistive device (cane, quad cane)

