 - Stroke Impact Scale (SIS)

Overground assessments will be taken during week one (Pre Testing), week two (Gait Assessments before/after Intervention and Post Testing on Day 5) and week three (Follow Up) of study procedures.

The **Overground Assessment** will occur as per the following schedule:

- ✓ **Week 1:** (Pre Test) Participant sessions will include ***gait assessments, balance assessments and self-assessment*** (Day 1 only) for each of three visits during the first week of study participation.
- ✓ **Week 2:** (Intervention) Participants will repeat ***gait*** assessments before and after each daily intervention session. On day 5 after study intervention, participants will be given a 10-15 minute seated rest break, and ***all (gait, balance, and self assessment)*** assessments will be repeated. These will be recorded as Post Test.
- ✓ **Week 3:** (Follow Up) Participants will complete ***all (gait, balance and self assessment)*** assessments.

** Denotes primary outcome measure.

- Participant will complete the 'Informed Consent' process prior to initiating any assessment or study related procedures.
- A physical therapist and at least one other member of the research team will be present to perform all assessment procedures.
- Participants' height and weight will be measured and recorded on CRF_TPAD_Form_03a (See attached).
- Any incidents with patient safety** during assessment sessions will be reported on CRF_TPAD_Form_03/03a/03b.
- Any missing visits** of the assessment sessions will also be noted on CRF_TPAD_Form_03/03a/03b.

1. *Gait Assessments*

Gait variables recorded include:

- Percentage of time in Stance phase of gait cycle (for each limb individually)**
- Percentage of time in Swing phase of gait cycle (for each limb individually)
- Percentage of time in Double Support phase of gait (net for both limbs)
- Stride Length (for each limb individually)
- Stride Velocity (for each limb individually)

A 14-meter course will be measured along a quiet hallway. The middle 10-meter segment of this course will be marked. Gait measures will be recorded during a series of three, 10 meter walk tests (10MWT) using the APDM® inertial based sensors.

A. **Set up:**

[figure not shown]
- a. Turn on MacBook Pro (Mid 2015, Apple®, Inc.) laptop and login with the User Name “*NRR_Lab*” and Password “*[name]*”.
- b. Secure the Access Point in the accompanying stand, and attach to the MacBook Pro laptop via the (18 inch) Micro USB cable provided.

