**Table 1 key for time points when variables are measured.**

1=Pre-Testing; 2=Prior to daily treadmill intervention; 3=Baseline on treadmill;  
4=Tethered TPAD Treatment; 5=Post Treatment on treadmill; 6=Post Overground  
Training; 7= Post Testing; 8=1-Week Follow Up Testing

Domain to be Measured	Outcome Measure	Variable Name	Time Required	When
Measures of Participation and Overall Health				
1. Adherence	Attended Visits	ADHER	1 minute	1,2,7,8
Measures of Activity				
2. Perceived Tolerance	Perceived Exertion	RPE	1 minute	2,3,4,5,6
3. Physiological Tolerance	Heart Rate	HR	1 minute	2,3,4,5,6
Measures of Body Functions				
4. Load Symmetry	Load Force	Fz	1 minute	3,5
Overground Spatiotemporal Measures of Gait				
5. Stance Symmetry	Symmetry Ratio - Stance Time	STANCE	15 minutes	Measured Simultaneously 1,2,6,7,8
6. Swing Symmetry	Symmetry Ratio – Swing Time	SWING		
7. Time in Double Support	Double Limb Support Time	DS		
8. Stride Length Symmetry	Symmetry Ratio – Stride Length	StrLENSYM		
9. Stride Length	Mean right/left -Stride Length	StrLENGTH		
10. Stride Velocity	Mean right/left -Stride Velocity	StrVEL		
11. Gait Velocity	Time of 10MWT	10WTIME		
12. Balance	Berg Balance Scale	BBS	20 minutes	1,7,8

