### ***3.4 Stride Length Symmetry Ratio***

Descriptive statistics (Mean (SD)) will be calculated and reported. Mean values of Stride Length Symmetry ratios will be analyzed using repeated measures analysis of variance (ANOVA) to compare to compare the mean of the pre-test measures to measures at post-test and follow up. Bonferonni corrections will be used to control for multiple comparisons. Effect sizes, and 95% confidence intervals will be calculated and reported with the F/Z statistic and p value. A graphical representation of the data will also be reported. Similar to stance and swing symmetry and double limb support, a linear regression model of daily change over time will be created using change scores from the mean of the three Pre Test measures to Day 1 of training. Within day changes for each of the five training days and changes from daily Pre Testing and from daily Post Testing will also be examined with a regression over time. Results of the regression models will

be used to determine the presence of a significant change over the course of the intervention and will be reported with the corresponding slope.

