### ***3.6 Stride Velocity***

Descriptive statistics (Mean (SD)) will be calculated and reported. Mean values of Stride Velocity will be analyzed using repeated measures analysis of variance (ANOVA) to compare to compare the mean of the pre-test measures to measures at post-test and follow up. Bonferonni corrections will be used to control for multiple comparisons. Effect sizes, and 95% confidence intervals will be calculated and reported

with the F/Z statistic and p value. A graphical representation of the data will also be reported. Similar to stance and swing symmetry and double limb support, a linear regression model of daily change over time will be created using change scores from the mean of the three Pre Test measures to Day 1 of training. Within day changes for each of the five training days and changes from daily Pre Testing and from daily Post Testing will also be examined with a regression over time. Results of the regression models will be used to determine the presence of a significant change over the course of the intervention and will be reported with the corresponding slope.

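### The stride length symmetry ratio is about 1 by geometry on a straight walk, so its planned analyses cannot show whether spatial symmetry improved overground

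*SAP*

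**What the plan says.** Protocol VI.C (Gait Assessments) records "Stride Length (for each limb individually" and "Stride Velocity (for each limb individually" along a hallway course of 14 m with the middle 10 m marked, three walks per assessment. Step length is not among the recorded variables.

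SAP 4.2.2 averages the three walks and then states "Symmetry ratios will be calculated from the mean values as follows". For stride length the definition is "StrLENSYM Symmetry Ratio = (Stride Length Paretic/Non-Paretic Limb". SAP Study Outcomes 2.3 puts this ratio among the secondary measures of transfer to overground gait. SAP Statistical Analyses 3.4 says "Mean values of Stride Length Symmetry ratios will be analyzed using repeated measures analysis of variance (ANOVA", comparing the pre-test mean with post-test and follow-up, with Bonferroni-corrected comparisons and several regressions over time. Sections 3.7 (Gait Velocity) and 3.8 (Balance) also name the stride length symmetry ratio as the analysed variable, apparently through copied text.

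The protocol's secondary list (IV.B) also contains "Stride Velocity Symmetry". The SAP has no such ratio. Its Table 1 lists "Mean right/left -Stride Velocity", and 3.6 says "Mean values of Stride Velocity will be analyzed using repeated measures analysis of variance (ANOVA".

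**The concern.** Spatial asymmetry after stroke is a difference between the paretic and the non-paretic step. A stride runs from one contact of a foot to the next contact of the same foot, so it contains one step of each kind. Dividing one limb's mean stride by the other's cancels the quantity of interest.

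This matters because the SAP's rationale is that two earlier studies with the device improved treadmill loading without transfer to overground measures. Stride length symmetry is the only overground symmetry ratio in the SAP that is spatial; stance and swing are temporal. If it cannot move, the trial has no working measure of overground spatial symmetry, although the SAP plans a full set of tests on one.

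**Working it through.** The documents give no expected value, SD or power for this ratio, so there is no planned figure to reproduce.

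**Inputs from the documents.** Ratio of per-limb means over three walks (SAP 4.2.2); 14 m course with the middle 10 m marked (Protocol VI.C); three pre-test visits and one post-test visit; 10 expected completers (Protocol, Participants); significance at 0.05 (SAP Statistical Analyses).

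**Assumptions not in the documents.** Step lengths, step variability, start and stop behaviour, and no sensor error.

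**1. Identity.** Let a_k be the k-th paretic step and b_k the non-paretic step that follows it.

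- Non-paretic stride k = a_k + b_k
- Paretic stride k = b_k + a_(k+1)
- Over n strides, paretic sum minus non-paretic sum = a_(n+1) − a_1
- Ratio of means = 1 + (a_(n+1) − a_1) / Σ(a_k + b_k)

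Both terms in the numerator are paretic steps, so the asymmetry drops out. In steady walking the numerator has mean zero. Stride time is likewise the sum of the same two step times, so a stride velocity ratio is also about 1.

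**2. Size of the remainder.** With an assumed step SD of 0.02 m and about 10 m of strides:

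- numerator SD = √2 × 0.02 = 0.0283 m
- per walk, 0.0283 / 10 = 0.0028
- averaged over three walks, 0.0028 / √3 = 0.0016

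With a step SD of 0.04 m the same steps give 0.0033. A simulation of 5,000 participants with steps of 0.55 m and 0.35 m (step ratio 0.55 / 0.35 = 1.57) gave a mean stride ratio of 1.000 with SD 0.0017 and 0.0034, in agreement.

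**3. Range of step asymmetry.** A second simulation assumed strides of 0.7 or 1.0 m, a step coefficient of variation of 6%, and step ratios from 0.6 to 1.6.

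| Strides used | Mean stride length ratio | SD per visit | 95% of visits |
|---|---|---|---|
| Middle 10 m | 1.000 | 0.002 to 0.003 | 0.994 to 1.006 |
| Nearly all 14 m, with start and stop | 0.993 to 1.008 | 0.009 to 0.010 | about 0.975 to 1.026 |

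Over the middle 10 m the stride velocity ratio was 1.000 with SD 0.003 to 0.004.

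**4. Plausibility.** A true stride ratio of 0.90 would leave one foot 10 × (1 − 0.90) = 1 m behind the other after 10 m. On a curve, with an assumed step width of 0.2 m, it would need a radius of 0.1 × (1 + 0.90) / (1 − 0.90) = 1.9 m. A straight hallway walk excludes both.

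**5. Power.** With 10 participants, an assumed 0.9 m stride and a step ratio improving from 0.7 to 0.9, a paired t test on the stride ratio (mean of three pre-test visits against post-test) rejected in 5.1% of 1,500 simulations. The Monte Carlo standard error is √(0.05 × 0.95 / 1,500) = 0.6 percentage points, so this is the false positive rate. The SAP's three-level ANOVA was not simulated here, but it tests a mean that does not depend on the step ratio, so the same reasoning applies.

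**6. Power if the whole path is used.** Start and stop strides let a little asymmetry through. In the 1.0 m stride case, moving the step ratio from 0.6 to 0.8 moved the mean stride ratio from 1.0076 to 1.0035, a shift of −0.0041 for a true change of 0.20.

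- SD of the change = √(0.0096² / 3 + 0.0097²) = 0.0112
- standard error = 0.0112 / √10 = 0.00353
- −0.0041 / 0.00353 = −1.16, which on 9 degrees of freedom gives about 18% power, two-sided

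In the 0.7 m case the shift is 1.0008 − 1.0014 = −0.0006 and power is about 5%.

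**The case against.** The geometry is hard to dispute. The fair objections concern consequence and precision.

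- **A reader might infer that a null result here will be declared failed transfer.** The documents do not say so. SAP Specific Objectives rest preliminary efficacy on load force and stance time symmetry, and Study Outcomes 2.2 makes stance symmetry the primary transfer measure. Swing symmetry, double support, mean stride length, mean stride velocity and gait velocity are also free of the identity. What stands is that a null could be misread, because the SAP describes earlier null overground results as lack of transfer.
- **A ratio of 1.000 with SD 0.002 to 0.003 is too precise.** This stands. It rests on assumed steps and on the middle 10 m. In Protocol VI.C sensor recording starts before the walk begins, only the stopwatch is tied to the 10 m segment, and the available text does not restrict the sensor data to that segment. The wider range is the safer one to quote. It reflects mostly edge strides.
- **A reader might infer that any significant result must be sensor noise.** That is too narrow. Chance, edge strides and starting or stopping could also produce one.
- **A reader might extend the fault to the SAP's stride velocity analysis.** SAP 3.6 analyses mean stride velocity, which is sound. Only the protocol names a velocity symmetry outcome, and it leaves analysis to the SAP.

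**Conclusion.** The point holds for one secondary outcome. On a straight walk the stride length ratio is about 1 whatever the step asymmetry. This follows from the definition and needs no assumption beyond steady straight walking. The planned test has power near its 5% false positive rate when steady strides are used. If whole-path strides are used, power could reach roughly 18% in the most favourable case worked above, through start and stop effects and with a shift of only 0.004. The numerical spreads rest on the assumed stride lengths, 6% variability and absence of sensor error.

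No primary outcome, eligibility rule, or safety or feasibility conclusion is affected. What the trial loses is any valid statement about overground spatial symmetry. The stride velocity item is a mismatch between the two outcome lists, not a faulty analysis.

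**What to change.** 1. In SAP 3.4, remove the ratio from inference: the ANOVA, the Bonferroni comparisons and the regressions. Keep it at most as a sensor quality check with expected value 1.00, and align Study Outcomes 2.3, Table 1, 4.2.2 and the protocol's secondary list (IV.B).
2. If the sensor export gives step length, which the documents do not say, define a paretic to non-paretic step length ratio and analyse that instead. Otherwise state that overground spatial symmetry is not assessed.
3. In SAP 3.7, replace the stride length symmetry ratio with gait velocity from the 10 m walk as the analysed variable.
4. In SAP 3.8, delete the duplicated stride length symmetry block. Its daily regressions could not apply to the Berg scale, which is measured only at pre-test, post-test and follow-up. If Bonferroni correction is intended for the Berg comparisons, restate it in the text that names that scale.
5. Delete stride velocity symmetry from Protocol IV.B, since it too is about 1 and the SAP analyses only mean stride velocity. SAP 3.6 needs no change.

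The cost is wording in both documents and the loss of the secondary analyses of one ratio. No visit or primary analysis changes; a step length ratio might need extra data processing.

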#### **4.2.3 Balance Measure**

*Berg Balance Scale*

Variable = **BBS**

**Assessed at time points 1,7, and 8.**

This assessment is a 14-item test that has been validated in various populations (including individuals post stroke) to measure balance. The items are performed in either seated or standing postures, and the total score reflects a quantitative measure of balance.

#### **Scoring**

Each of the 14 items is scored individually based on a numeric scale of 0 (unable to perform) to 4 (able to maximally perform task). The total score reflects a summation of each of the individually scored items (maximum score = 56). All BBS examinations were video recorded, and an external rater, blind to the study protocol and to testing order, scored the test based on the video recording.

### **5. Missing Data**

Missing data will be identified as soon as possible after data collection and an attempt made to get as much information as possible about the data point in question.

Missing data will be excluded from the final analysis. If a single variable has more than 15% of data missing, this variable will not be included for interpretation in the final results.

## **6. Outliers**

Any unusual data points or measures will be reviewed for authenticity both during and after the trial. The influence of any outliers on the primary analyses will be checked. If any outliers are removed from the dataset, this will be reported along with the rationale for exclusion.

## **7. Study/Analysis Time Frame**

The total time for individual participation in the study is three weeks. The participant will complete three initial (pre-test) assessments within one week. The following week s/he will receive the five-day training and the post-test assessment. The individual will return the third week for a single follow up assessment.

## **Statistical Analyses**

Statistical assumptions and normality will be tested prior to running statistical analysis for measures of treatment tolerance, force symmetry, spatiotemporal gait parameters including stance symmetry and balance. A *p value* of 0.05 or lower will be considered statistically significant for all analyses.

### **1. Descriptive Analysis**

We will report descriptive statistics (age, gender, side of impairment, time since stroke event, baseline functional ambulation scoring, and stroke impact scale scores) summarily. Graphs and/or tables will be used to represent descriptive data.

## **2. Analysis of Primary Outcomes**

### **2.1 Primary Outcomes of Feasibility**

#### ***2.1.1 Safety***

All adverse events (related to participation) including any injuries or falls will be reported summararily in the final report.

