BACKGROUND: Hemiparesis, spasticity and reduced motor control are typical impairments after stroke and commonly contribute to motor deficits that affect gait. These deficits manifest as reduced velocity, decreased cadence and asymmetries in temporal, spatial and force parameters during ambulation. Robotic-based therapies have been used to increase gait velocity and reduce asymmetry in a population of individuals after stroke, however these therapies have demonstrated results similar to that of conventional training. This is possibly due to guided-assist control strategies used to deliver robotic training, which strategies limit participant involvement and thus constrain motor learning.

The TPAD is a robotic device that employs actuated tethers at the user's pelvis to guide the user's pelvis along a pre-set movement trajectory. The TPAD tethers can be configured in an infinite array of possibilities, and most recently have been used to increase loading onto the paretic limb in a population of individuals after stroke. While other robotic devices guide the limb through the motor trajectory, and constrict the participants ability to participate in the motor planning and movement execution, the TPAD promotes weight shifting, but allows an individual to freely move the limb and to navigate spatiotemporal aspects of training independently. Further, if coupled with overground to focus on addressing a specific task goal, this device may prove useful to improve symmetry in individuals after stroke.

OBJECTIVES: The purpose of this study is to evaluate the overall feasibility in terms of safety, treatment tolerance and adherence as well as address preliminary efficacy of implementing a treatment paradigm using the TPAD with visual feedback and overground training to reduce load asymmetry on the treadmill and promote increased stance symmetry on the paretic limb during overground gait.

PARTICIPANTS: To account for 20% attrition, a total of 12 individuals in the chronic (>6 months) stages post stroke will be recruited from a voluntary stroke research registry with anticipation that 10 individuals will complete participation.

DESIGN: A non-randomized pilot study of feasibility will be used to establish the preliminary efficacy of using the TPAD in combination with overground training to reduce load force asymmetry in this population.

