#### **Rationale for current trial:**

A detailed description of the TPAD can be found in the Standard Operating Procedures Manual. Prior experiments have used the TPAD to improve loading onto the paretic limb in a post-stroke population. Initial studies using the TPAD in this population delivered a short duration of TPAD training that provided guided loading directly onto the paretic limb during a single training session. Measures of perceived exertion using the Borg Scale were recorded, as

was the number of falls sustained during study participant. Results showed no falls and Borg Scale measures indicated this was a feasible training paradigm for individuals post-stroke. Further, results also demonstrated that participants were able to increase loading onto the paretic limb during training, and these gains were maintained even when TPAD forces were removed during a post-training interval on the treadmill. However, gains made on the treadmill did not transfer to improvements in overground spatiotemporal gait measures.

A follow up experiment looked at the effects of TPAD training in two different training paradigms over the course of a five-day training. For this study, the TPAD tethers were arranged to apply a horizontal force in the anterolateral direction to induce a weight shift onto the limb during the stance phase of gait without downward forces that passively increase loading onto the limb. Similar to the previous study, the goal of the TPAD training was to improve load symmetry between the two limbs. In addition to the application of TPAD forces, augmented visual feedback was supplied during the course of the training period. This feedback reflected the amount of loading onto the paretic limb in real time and provided a visual representation of the task goal. While the details of the two training paradigms will not be discussed here, results were equivocal between the two paradigms. Both training paradigms showed improvements in load forces on the paretic limb, and thus improved load symmetry between the two limbs. Further, in both training paradigms these improvements were retained after force tethers were removed on the treadmill. However, neither of these training models proved effective at promoting transfer of increased load force symmetry from treadmill training to gains in overground spatiotemporal gait parameters.

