### **SPECIFIC OBJECTIVES:**

1) Is this five-day intervention using the TPAD and incorporating faded visual feedback and overground walking feasible in terms of safety, treatment tolerance and adherence in individuals with chronic stroke who present with gait asymmetry?

As a measure of treatment efficacy, this study will specifically address the following questions:

2) Is this treatment paradigm effective at improving load force symmetry over the course of five training sessions as measured from Baseline Day one to Post Training Day five?

3) Is this training paradigm effective to promote transfer and improve stance time symmetry in over ground gait as measured from a mean of the three days in Pre Testing to Post Testing?

The presence of preliminary efficacy in the prior two questions, coupled with measures of safety, treatment tolerance and adherence will be used to answer the over arching question of feasibility and preliminary efficacy.

[figure not shown]

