**Figure 1: Trial Schema**

A total of 12 participants will be enrolled to participate. Participants will be assessed over a series of three over ground Pre-Tests by a member of the study team. On completion of over ground Pre Tests, symmetry ratios (paretic/non-paretic limb) will be calculated for percentage of time in stance phase. The mean value of these ratios will be calculated. As the minimal detectable change (MDC) for time in stance has been identified as 0.09, participants will be required to have a mean symmetry ratio of 0.90 or less of time in stance after Day one of Pre Testing to be considered eligible for participation in the trial. Details of other

inclusion/exclusion criteria can be found in the Standard Operating Procedure Manual for this study. The details of data collection are outlined here with an associated plan for statistical analysis.

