### **Study Outcomes**

#### **1. Feasibility**

The primary feasibility outcomes will include an evaluation of safety, tolerance to treatment, and adherence over the course of the trial.

**1.1.** Safety of the intervention will be assessed by recording the number of adverse events (AE) and/or serious adverse events (SAE) that occur throughout the duration of the trial and will be reported as summary data.

**1.2** Treatment tolerance will be measured primarily by rates of perceived exertion (RPE) and secondarily by the percentage of maximum heart rate (HRmax) throughout daily training sessions.

**1.3** Rates of adherence will be presented as a proportion of visits attended out of the total study visits. Participants who are not able to complete at minimum four out of the five training visits (80% adherence) will not be included in the final data analysis.

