#### ***2.1.3 Adherence***

The proportion of adherence to the intervention will be reported descriptively as a percentage of total visits.

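### Safety and adherence are primary feasibility outcomes but get no participant-level count or confidence interval, and the SAP does not exempt them from its 4-of-5-visits exclusion

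*SAP*

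**What the plan says.** The SAP (Study Outcomes, section 1) states: "The primary feasibility outcomes will include an evaluation of safety, tolerance to treatment, and adherence over the course of the trial". Under Specific Objectives, evidence of efficacy "coupled with measures of safety, treatment tolerance and adherence will be used to answer the over arching question" of feasibility. No numerical criterion for feasible or safe is given.

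The planned analyses of the two outcomes are short:

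- Safety (Statistical Analyses 2.1.1): "All adverse events (related to participation) including any injuries or falls will be reported summararily in the final report". Study Outcomes 1.1 describes the measure as a number of events.
- Adherence (Statistical Analyses 2.1.3): "The proportion of adherence to the intervention will be reported descriptively as a percentage of total visits".

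By contrast, Statistical Analyses 2.2.1, 2.2.2 and 3.1 to 3.8 call for 95% confidence intervals for load force, stance symmetry and all the secondary gait and balance outcomes.

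Study Outcomes 1.3, which is the adherence item itself, removes participants with fewer than four of the five training visits from the final analysis. The text under the trial schema repeats the rule. Neither place says whether safety and adherence are exempt.

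On numbers, the SAP says "A total of 12 participants will be enrolled to participate", and the Protocol (Study Population) recruits 12 while "anticipating 20% attrition, or that at least 10 participants will meet criteria and complete study participation".

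**The concern.** The outcomes on which the main conclusion rests get the least informative analysis in the SAP. With 10 to 12 people, an absence of events leaves a wide range of true risks open, and nothing in the planned report would show that range. A count of events, or a percentage of visits, also does not tell the reader how many people were affected or how many completed the course.

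The denominator adds to the problem. If the 4-of-5 rule is applied to adherence, the people with poor attendance are removed before attendance is summarised. If it is applied to safety, someone who stopped early could drop out of the count. Protocol section VII lists both low attendance and an injury that prevents completion as grounds for withdrawal, so the two can coincide.

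SAP Study Design describes the feasibility measures as important for planning later randomised trials. A summary without limits, on an unclear denominator, is weak material for that purpose.

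**Working it through.** **Inputs.** Planned enrolment 12 (SAP, trial schema; Protocol, Study Population). Anticipated completers 10, attrition 20% (Protocol, Participants and Study Population). Minimum training attendance 4 of 5 visits (SAP, Study Outcomes 1.3). The SAP sets significance at 0.05 without stating sidedness, so two-sided 95% intervals are assumed and one-sided limits are shown beside them.

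**The plan's own figure.** "To account for 20% attrition, a total of 12 individuals in the chronic (>6 months) stages post stroke will be recruited". Multiplying, 10 × 1.20 = 12, which reproduces it. Dividing, 10 / 0.80 = 12.5, so 13; and 12 × 0.80 = 9.6 expected completers. The difference is immaterial here, and 12 and 10 serve as the two denominators.

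**Safety: upper limit for the per-person risk of at least one adverse event when nobody has one.**

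| Method | Formula | n = 12 | n = 10 |
|---|---|---|---|
| Exact, two-sided 95% | 1 − 0.025^(1/n) | 26.5% | 30.8% |
| Exact, one-sided 95% | 1 − 0.05^(1/n) | 22.1% | 25.9% |
| Rule of three | 3/n | 25% | 30% |
| Wilson, two-sided 95% | score interval | 24.2% | 27.8% |

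The choice of method moves the limit by a few points and does not change the message.

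**Chance of seeing nobody affected, (1 − p)^n.** The values of p are assumed, since the documents give no expected rate.

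- p = 10%: 0.9^12 = 28%; 0.9^10 = 35%.
- p = 20%: 0.8^12 = 7%; 0.8^10 = 11%.

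**Adherence: floor created by the exclusion.** If only people with at least 4 of 5 training visits remain, each contributes at least 4/5 = 80%, so the pooled training-visit figure cannot be lower than 80%.

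Illustration with assumed attendance: ten people attend 5 of 5 and two attend 3 of 5.

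- Visits, everyone counted: (10 × 5 + 2 × 3) / (12 × 5) = 56/60 = 93%.
- Visits, after the exclusion: 50/50 = 100%.
- Participants completing at least 4 of 5: 10/12 = 83%.

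**Adherence: precision of the participant-level proportion (Clopper-Pearson 95%).**

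- 10/12 = 83%: 51.6% to 97.9%.
- 12/12: 73.5% to 100%.
- 10/10: 69.2% to 100%.

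These are illustrative completion rates, not intervals for the SAP's visit-level percentage. Visits are clustered within 10 to 12 people, so a simple binomial interval on visits would be too narrow. That is why the participant is the right unit.

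**The case against.** Descriptive safety reporting is normal in a single-arm pilot of 12, and reporting in summary does not rule out a per-participant count. Incidents and missed visits are recorded on forms filed by participant code, so the extra figures could be derived at reporting with nothing lost. This stands, and it limits the weight of the point. It does not remove it: an exact interval is itself descriptive, and the SAP already plans intervals for every efficacy outcome in the same few people.

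A reader might infer that the plan will treat zero events as proof of safety. No section says so. The nearest text concerns an earlier study of the device: "Results showed no falls and Borg Scale measures indicated this was a feasible training paradigm for individuals post-stroke". That rests on falls and exertion together, the SAP's summary of the prior work is worded cautiously, and the number of participants in that study is not given.

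A reader might also take 26% to 31% as the share of patients likely to be harmed. It is not. It is the upper end of an interval under a hypothetical zero count, and the adverse events listed in Protocol section X include dizziness and severe fatigue. With so broad a list, the documents give no reason to expect zero events.

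Nor do the documents show that the 4-of-5 rule will be applied to safety or adherence. They are silent on it.

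Finally, the Protocol's anticipated shortfall from 12 to 10 can include people who fail eligibility, because the stance criterion is judged after the first pre-test day. Counting them as non-adherent would be wrong, and the denominator in the fix allows for this.

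**Conclusion.** The point holds as a gap in precision and in the definition of the denominator; nothing in the plan is miscalculated. With nobody affected, a true per-person risk of at least one adverse event as high as 26.5% (n = 12) or 30.8% (n = 10) stays compatible with the data at the exact two-sided 95% level, or 22% to 26% one-sided. Training-visit adherence would have a floor of 80% if the exclusion in Study Outcomes 1.3 is applied to it.

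The safety limits assume that participants are independent and that 10 to 12 people form the denominator; they apply to whatever events the SAP counts, which section 2.1.1 restricts to those related to participation. The adherence floor depends on how a silent text is read. This is a cheap improvement that should be made, of minor to moderate weight. It does not call the design of the pilot into question.

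**What to change.** - **Section 2.1.1.** Beside the event count, report the number of participants with at least one adverse event, fall or serious adverse event, out of all who began study procedures, with the Clopper-Pearson 95% interval.
- **Section 2.1.3.** Beside the visit-level percentage, report the number completing at least 4 of 5 training sessions, out of all eligible participants who entered training, with the same kind of interval.
- **Study Outcomes 1.3.** State that the exclusion for low attendance does not apply to safety or adherence.
- **Feasibility conclusion.** Quote the interval limits along with the point values.

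The two denominators differ on purpose: an incident can occur during pre-testing, whereas adherence to training is only defined for those who were eligible and started it.

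The cost is a few sentences in the SAP and two exact intervals, from data already collected on the participant forms. The feasibility statement will read less favourably. The change does not supply a threshold for calling the programme feasible; it only makes visible how much 10 to 12 people can show.
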